## 7. Research Plan for Study 2:

- **Study Design.** Study 2 will address Specific Aim 2 and will involve a nested, group-randomized controlled design, recruiting adolescents from ASPs, such as the Boys and Girls Clubs in Florida. In a 2 (condition) by 4 (time) design, 4 clubs minimum will be randomly assigned to one of two conditions named “ASPIRE” and “GSA-ASPIRE-Network”. Additional ASPs may be recruited in case sample size is not reached.
- Similar to a “wait-list” group, participants in the “ASPIRE” group will receive the GSAs and Network (GSA-Network) portions of the program about 4 weeks following Survey Assessment 4 (A4), between Assessments 5 and 7, in 5 to 7 sessions (5 regular sessions and up to 2 booster sessions). This will include 4 additional assessment points following Assessment 4. With 4 additional assessment points following Assessment 4, we will get to examine improvement over time following participants' engagement in the social features of the program. Participants in the ASPIRE-only group did not have the opportunity to engage with these social features of the program during the Fall.
- To assess long term success among participants in the “GSA-ASPIRE-Network” group, 2 assessment points will be added to this group (A5 and A8 only).
- Survey assessments A5 through A8 will be the same as the network assessment survey (Appendix 4).

- **Eligibility.** An ASP is eligible if it provides internet connection at its club and houses at least 10 adolescents. Adolescents will be eligible if (1) they are of ages 11-18 years, (2) they are members of ASP, (3) they are English-speaking, and (4) have not participated in an educational program about tobacco in the last year. Adolescents with developmental disability, mental or physical, are not excluded from the study. However, they will only be able to participate if (1) they understand the information presented to them in the consent document, and (2) they believe they are capable to engage in the board game, use the internet, and answer survey questions.
- **Methods for Study 2.** The following section describes the methods being used and step-by-step procedures to conduct the study.

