- **Final design of the GSAs during COVID-19:** In case ASPs are not allowing their adolescent members meet in person at their sites, we plan to use a web-based version of the GSAs that we will develop with a team of computer scientists. The computer science team will create the web-based GSAs to incorporate all aspects of the GSAs created by TESA. While overseen by the Integrated Risk Management (IRM) team at the University of Florida, the computer science team will develop the web-based version while complying with UF security and privacy guidelines and policies. The web-based GSAs will have a secure built-in video-conferencing system to ensure that participants can communicate with one another as well as the research team. The web-based GSA will also have the ability to record sessions, administer questionnaires, and collect activity entries for the purpose of data collection. Appendix 12 shows a mock picture of what is envisioned for the web-based GSAs. Any changes in the web-based GSAs based on the recommendations of IRM and the computer science team will be described in a revision to the study before implementing. In addition to the web-based GSA, the TESA team may make the boardgame playable online by creating the boardgame in an online portal for virtual boardgames known as Tabletopia. The use of Tabletopia will not be done without a risk assessment completed by Integrated Risk Management (IRM).

- **Connection with ASP sites:** At first, as many as a minimum of 20 ASPs such as the Boys and Girls Clubs in Florida and schools such as PK Yonge school will be approached for this study. The PI and/or study staff will attend ASP sites, in order to present the study to program directors and describe to them the study procedure.

Once ASPs are recruited, we will obtain letters of support (Sample in Appendix 0) or a Contract for Services (Sample in Appendix 15) from these ASPs. Signed letters of support or Contract for Services will be submitted to IRB. We will not move forward with data collection from adolescents unless signed letters of support are obtained from the ASPs.

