- Parents will use the iPad to review the consent and provide an electronic consent. Adolescent will also assent on the iPad. However, paper consent forms will be available in case parents or adolescents prefer a paper-based form. Both parents and adolescents will receive a copy of the consent document for their own records.
- For parents that are hard to reach, ASP staff will send the adolescent home with a one-page parent permission consent form for the parent to review and sign. Once parental permission is obtained, research staff will review the child assent with the adolescent and obtain their assent.
- Adolescents ages 11-17 will review and sign the child assent with study staff either in-person or remotely.

For sites that require parent permission for 18-year-old adolescents to participate in extracurricular activities, ASP staff will send the adolescent home with an informed consent form or a one-page parent permission form for the parent to sign. Once the parental permission is obtained, research staff will review the informed consent form or the one-page consent form specific to 18-year-old adolescents with the 18-year-old adolescent.

A separate consent form has been created for 18-year-old adolescents. Following our announcement at the ASP, if an adolescent who is 18 years of age expresses interest in the study, we will approach this individual during breaks at the ASP to go in detail over the consent form.

- It is expected that 800 adolescents and their parent/legal guardian from about 15 ASPs will be interested and eligible. Parental permission and child assent forms will be presented in-person, and in details by a study staff or the PI. A staff member of the ASP will act as witness during consent.
- After recruitment, we will schedule dates with the ASP in order to conduct the study.
- **Consent procedure for study 2 during COVID-19:**  
Due to COVID-19, we will be reviewing the study information and assents/consent forms with adolescents and parents remotely via phone call or Zoom should the ASP not allow research staff, adolescents, or their parents inside the facility. Research staff will contact participants using Cisco Jabber.

If parents and adolescents are allowed to be at the ASP facility, research staff will review the consent form with parents and adolescents in person. Parents and adolescents will be given the option of signing a paper consent form to review and sign with the guidance of PI and/or study staff.

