- **Intervention details:** The first session of the assigned intervention (ASPIRE or GSA-ASPIRE-Network) will occur three to five days after orientation (depending on the ASP's availabilities).
  - › In the ASPIRE condition (other treatment), participants will engage in five 70-minute sessions of ASPIRE spread over a period of 5 weeks (1 session per week). During each session, participants will alternate between 10 minutes of ASPIRE use and 5-minute breaks.
  - › In the GSA-ASPIRE-Network condition (intervention), on the other hand, participants from each club (expected to be between 24 and 50 participants) will be purposely seated in groups, with 3 to 6 adolescents per group. Participants' group allocation will be determined based on findings from social network analysis (details below). Each group will engage in five 70-minute sessions of ASPIRE spread over 5 weeks (1 session per week). During each session, participants will either receive ASPIRE, or the GSAs, or both. Along with the game board, GSA content will be presented to participants via the "Kahoot! 360 Pro" platform. Study data will not be captured nor stored on Kahoot. Participants will not complete any assessment question of identifiable questions via "Kahoot!". They will engage in the program as a team. After each session, with a timeline of a week, participants will have the opportunity to engage in off-session activities at their own pace. These activities will allow participants to practice what they learn during the sessions. To receive credit for completing the activities, participants will be asked to keep track of their progress in these activities and present evidence of completing the activities. To this end and depending on the activities, they may record themselves completing the activity via photo or video and submitting the recording to the research team via the secure system REDCap. Recording and submitting the photos or videos will not be required to participate in the research project, and alternative methods of presenting evidence of activity completion will be provided. If participants choose to submit videos or photos for their activities, they will be asked to capture these videos and photos without having a non-participant in the background. If a non-participant is visible in the background, the recording will be censored to remove the non-participant.

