Susceptibility to use tobacco is a clinical and epidemiological screening questionnaire of 3 items that has been shown to be the most potent predictor of actual tobacco initiation among adolescents. The continuous version of this scale is termed “intention to use tobacco”. Sample size and power have been calculated based on the hypothesized difference between groups that render participants in the GSA-ASPIRE-Network group non-susceptible to use tobacco, based on the “intention to use tobacco” scale and previous research.

Sample size calculation is done for H1 and satisfies H2. These power estimates are conservative. We will have more power using mixed-effect models. Sample size was calculated based on 2 clusters per arm, however, we will have more power with the proposed 8 clusters (4 clusters per arm). Considering that about 33% of adolescents generally intent to use tobacco, the required sample size is 300 participants. Considering 40% retention and 50 potential non-eligible, we will recruit 800 participants. In addition to this sample size, we will work to reach a representative Florida sample of adolescents. For the interviews, thematic saturation with adolescents is expected by 60 interviews (20% of the final 300 participants).

- **Quantitative data analysis for Study 2.** To test H1, a linear mixed-effect model (LMM) will be conducted to compare the conditions with respect to intention to use tobacco (continuous outcome variable), in a 2 (condition)  $\times$  4 (time) design. Using a second LMM, the 2 conditions will be compared over time with respect to positive social influence. In both models, intervention effects on outcome trajectories over time will be measured with the condition  $\times$  time interaction term. To test H2, a third LMM will be conducted with positive social influence as a mediator. Each individual will be modeled as a random effect nested within the club, club membership will be modeled as a random effect nested within treatment condition, and treatment will be modeled as a fixed effect. If manipulation checks indicate problems, particularly differences or similarities between arms that are not supposed to occur, we will control for such differences or similarities within our models.

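### The Study 2 sample-size text gives a club number, a club size, a recruitment total and an at-risk count per cluster that cannot all hold, and the 80% power for two clubs per arm does not survive club-level degrees of freedom

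*Combined protocol and SAP*

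**What the plan says.** All of the relevant text is in section 7, Research Plan for Study 2, of the combined protocol and SAP.

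- **Study Design:** "4 clubs minimum will be randomly assigned to one of two conditions". The next sentence adds that "Additional ASPs may be recruited in case sample size is not reached".
- **Connection with ASP sites:** the sponsor will approach "as many as a minimum of 20 ASPs such as the Boys and Girls Clubs in Florida" and schools.
- **Consent procedure:** "It is expected that 800 adolescents and their parent/legal guardian from about 15 ASPs will be interested and eligible". The COVID-19 version of the consent text gives 1000 instead, with no club number.
- **Intervention details, GSA-ASPIRE-Network arm:** "participants from each club (expected to be between 24 and 50 participants) will be purposely seated in groups".
- **Sample Size Considerations:** the power statement uses 2 clusters per arm, 25 adolescents with intention to use tobacco per cluster (n=100), ICC 0.3 and 80% power, two-sided at 0.05. It then says "we will have more power with the proposed 8 clusters (4 clusters per arm"), takes 33% as the at-risk share, requires 300 participants, and concludes: "Considering 40% retention and 50 potential non-eligible, we will recruit 800 participants".
- **Justification table for Studies 1 and 2:** splits the 800 into 300 completing, 450 who may discontinue and 50 for screening.

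**The concern.** Three club numbers appear (a minimum of 4, a proposed 8, about 15), and nothing says which one the 800 belongs to. With eight clubs, 800 recruits means 100 per club, twice the top of the expected range. The power inputs also assume more at-risk adolescents per cluster than a club of the expected size would contain.

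At an ICC of 0.3 the number of clubs drives the precision of the comparison, so this figure should be fixed before randomisation. The stated 80% power is attached to two clubs per arm, which is also the smallest design the protocol allows if the four clubs are split equally. A reader could take it that four clubs are adequate.

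**Working it through.** **Reproducing the plan's figures.**

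- Size chain: 100 / 0.33 = 303, or 300 with one third. 300 / 0.40 = 750. 750 + 50 = 800. This matches the justification table (300 + 450 + 50).
- Power, 2 clubs per arm, 25 at risk per club: design effect 1 + (25 - 1) x 0.3 = 8.2. Effective n per arm = 50 / 8.2 = 6.10. Standardised difference for positive social influence = (2.43 - 1.0) / 0.8 = 1.79; for intention = (1.3 - 0.17) / 0.5 = 2.26.
- A non-central t with df = 2 x 6.10 - 2 = 10.2 gives 80.4% for positive influence, which reproduces the stated 80%. The same method gives 94% for intention.

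**What clubs of 24-50 supply.** Read as enrolled counts, with 40% retention and 33% at risk, assumed equal in all clubs and both arms:

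| Clubs | Enrolled | Completers | At-risk completers |
|---|---|---|---|
| 4 | 96-200 | 38-80 | 13-26 |
| 8 | 192-400 | 77-160 | 25-53 |
| 15 | 360-750 | 144-300 | 48-99 |
| Stated | 800 recruited (750 enrolled) | 300 | 100 |

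With the documents' 20%-40% at-risk range, eight clubs give 15-64 at-risk completers. Fifteen clubs meet the chain only at 50 each: 15 x 50 = 750 and 750 x 0.40 = 300.

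**If 24-50 is a retained count.** Eight clubs give 192-400 completers (300 needs 37.5 per club) and 63-132 at risk at 33%. Recruitment before loss would then be 24 / 0.40 = 60 to 50 / 0.40 = 125 per club, or 480-1000 over eight clubs. On this reading the figure of about 15 clubs no longer fits: 750 / 15 = 50 enrolled per club, and 50 x 0.40 = 20 retained, below 24.

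**At-risk adolescents per cluster.** 24 x 0.20 = 4.8 and 50 x 0.40 = 20. The 25 used for power is therefore out of reach for any club of 24-50. At one third at risk it needs about 75 adolescents, and 75 / 0.40 = 188 enrolled if the 25 are completers.

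**Power on club-level df.** The design effect is as above and df = 2K - 2 for K clubs per arm. At-risk completers per club, m, run from 24 x 0.40 x 0.33 = 3.2 to 50 x 0.40 x 0.33 = 6.6.

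| Design | m | Effective n per arm | df | Positive influence | Intention |
|---|---|---|---|---|---|
| 4 per arm | 3.2-6.6 | 7.7-9.9 | 6 | 83-91% | 96-98% |
| 2 per arm, plan's inputs | 25 | 6.1 | 2 | 41% | 56% |
| 2 per arm | 3.2-6.6 | 3.9-4.9 | 2 | 30-35% | 41-49% |

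For positive influence at two clubs per arm, the choice of df moves 80% to 41%, and the smaller clubs move 41% to 30-35%. Most of the drop comes from the df.

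One corner of the eight-club design falls lower. With 24 enrolled per club and only 20% at risk, m = 24 x 0.40 x 0.20 = 1.92 and effective n = 4 x 1.92 / 1.276 = 6.0. Power on 6 df is then 73% for positive influence and 90% for intention.

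**The case against.** The strongest defence is that eight is not a fixed design. Four clubs is a floor, the next sentence lets programs be added if the sample size is not reached, at least 20 will be approached, and about 15 are expected to supply the 800. At 50 enrolled each, 15 clubs give exactly 750 enrolled and 300 completers. The sentence about more power with eight clusters is also correct on the plan's own effects and ICC.

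Much of this stands. A reader might infer that the trial can stop at four clubs, but the provision to add programs is tied to the sample-size target and nothing says recruitment may end at the minimum. A reader might also infer that 300 completers and 100 at-risk adolescents are unattainable with eight clubs. That holds only if 24-50 is counted before the 60% loss. The text describes adolescents seated in groups formed from the baseline network, which favours an enrolled count, but the documents do not say so.

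The defence does not remove the conflict. The provision to add programs is permissive and names neither the target that triggers it nor how many may be added. Fifteen clubs work only with every club at the top of its range, while a program is eligible with as few as 10 adolescents. The sample-size section itself names eight, and 25 at risk per cluster fits neither reading.

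**Conclusion.** The conflict is real. Eight clubs, 24-50 per club, 800 recruits, about 15 programs and 25 at-risk adolescents per cluster do not fit together, whether 24-50 is an enrolled or a retained count. As a headcount, eight clubs hold 192-400 adolescents, at most half of 800.

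The documents do not support a conclusion that the proposed eight-club design is underpowered. At the documents' average at-risk share of 33% it keeps 83-91% for positive influence and 96-98% for intention, the primary outcome. The point should therefore be corrected, but it does not undermine the proposed design. The statement that needs correcting on power is the 80% for two clubs per arm. On 2 club-level df this is about 41% for positive influence and 56% for intention with the plan's own 25 per cluster, and 30-35% and 41-49% with the 3-7 at-risk completers that clubs of 24-50 would supply.

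These figures assume that 24-50 applies to both arms, that retention and at-risk share are equal across clubs, that arms have equal numbers of clubs, and that power is counted on at-risk adolescents at a single comparison of means, as in the plan's own calculation. The mixed model over repeated assessments may change the power, but the plan gives no within-person correlation with which to work that out.

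**What to change.** 1. State one planned number of clubs per arm and one expected club size. Say whether 24-50 is an enrolled or a retained count and whether it applies to both arms.
2. Restate recruits, enrolled, completers and at-risk adolescents per club from that set. Make Study Design, Consent procedure (including the COVID-19 text), Intervention details, Sample Size Considerations and the justification table agree.
3. Recompute power for that set on club-level df, with the at-risk count per club that follows from it, over the 20%-40% range.
4. Do not quote 80% power for the four-club minimum. If the minimum stays, give its power on 2 df.
5. State which target triggers the addition of clubs (recruits, completers or at-risk completers).

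The cost is protocol wording and one recalculation. If eight clubs are kept and 24-50 is an enrolled count, the stated totals fall to 192-400 enrolled and 77-160 completers. If 800 recruits are kept on that count, 800 / 50 = 16 to 800 / 24 = 33.3, so 16 to 34 clubs are needed. In either case the power stated for the minimum design becomes less favourable.

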- **Adolescent Grouping.** To group adolescents during the GSA-ASPIRE-Network condition (details in Appendix 6), the variable indicating intention to use tobacco will be dichotomized (0=no intention; 1=some intention). At time 1, adolescents who intent to use or are using tobacco will be matched with 2 to 4 adolescents who are closest in distance and do not intent to use tobacco. This ratio is chosen based on previous research showing that 20%-40% of adolescents report some intention to use (average, 33%). If assignment of adolescents to group faces difficulties, we may rely on a continuous measure of intention to use tobacco. Adolescents who indicate intent/use will remain the minority in each group. This design should play a role in preventing at-risk adolescents from influencing their group peers.

The PI along with a statistical analyst and statistician will privately meet in-house at the department in order to make decisions about the intended groupings based on the network data. The study staff will not be present at these meetings. They will be blinded to the basis of the grouping. As a result, they will implement the groupings at the ASPs without knowing the basis of the grouping, thereby insuring that the intended groupings are achieved without disclosing its basis to the participants.

- **Sample Size Considerations for Study 2.** Summary statistics were obtained from the original trial. For H1, given 2 clusters per arm with an average of 25 adolescents who intent to use tobacco in each cluster (n=100) and intra-class correlation (ICC) of 0.3, 80% power is achieved using a two-sided test, with significance  $p<0.05$  to detect a difference in positive social influence in the ASPIRE arm of 1.0 and the GSA-ASPIRE-Network of 2.43 assuming a common standard deviation of 0.8. A difference will be detected

in intention to use tobacco in the ASPIRE arm of 1.3 and GSA-ASPIRE-Network of 0.17 assuming a common standard deviation of 0.5.

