#### • **Justification for number of participants for Study 1 and study 2**

	Study 1	Study 2	Studies Combined
Participants needed to complete study:	63	300	363
Additional participants enrolled but may discontinue:	30	450	480
Additional participants needed to undergo screening:	7	50	57
Total number of participants:	100	800	900

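### Study 2 plans for 40% retention but uses the loss only to raise recruitment; the H1 model's missing-data assumption is neither stated nor tested, although the final intention score may be missing for up to 60% of participants

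*Combined protocol and SAP*

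**What the plan says.** Section 7, Sample Size Considerations for Study 2, scales 100 adolescents with some intention to use tobacco up to a full sample using a 33% share, and concludes that "the required sample size is 300 participants". It then says: "Considering 40% retention and 50 potential non-eligible, we will recruit 800 participants". The table justifying the number of participants gives the same split for Study 2: 300 to complete, 450 under "Additional participants enrolled but may discontinue", and 50 under "Additional participants needed to undergo screening".

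For H1, Quantitative data analysis for Study 2 says that "a linear mixed-effect model (LMM) will be conducted to compare the conditions with respect to intention to use tobacco", over two conditions and four times, with the effect read from the condition-by-time interaction and random effects for individual and club. It names no analysis population, missing-data assumption, comparison of leavers with stayers, check of loss by arm, or sensitivity analysis. The only conditional adjustment follows from the manipulation checks, which the psychosocial survey collects at time 3 only, so they do not exist for anyone who left before then.

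Two other provisions create missing data. Section 9 destroys the information of a participant who discontinues over a concern with the intervention content. It also lets the investigator withdraw a participant for non-compliance, without saying that outcomes would still be collected.

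**The concern.** Inflating recruitment restores precision. It does nothing about bias if those who leave differ from those who stay.

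A mixed model fitted by likelihood uses partial records and is valid under missing at random: given arm and the intention scores already observed, leaving must not depend on the scores never seen. At a planned loss of this size, that assumption carries much of the final-assessment comparison.

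The protocol gives reasons why it could fail differently by arm. Only GSA-ASPIRE-Network has team seating and off-session activities, and adolescents who use or intend to use tobacco are deliberately kept a minority in each team. Tobacco-use status could plausibly predict both leaving and intention. It is measured at all four times but is not in the model.

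At stake is whether an H1 result, particularly a modest one, can be told apart from selective leaving.

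**Working it through.** **Inputs.** From Section 7: 300 completers, 40% retention, 50 non-eligible, a 33% share with intention, and expected intention scores of 1.3 (ASPIRE) and 0.17 (GSA-ASPIRE-Network) with SD 0.5. From the participant table: 300, 450 and 50.

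**The plan's own figure.**
- 100/0.33 = 303, which the plan gives as 300.
- 300/0.40 = 750; 750 + 50 = 800. This reproduces exactly.
- 450/750 = 0.60. Reading the figure as 40% loss would give 300/0.60 + 50 = 550, which matches neither text nor table. The 60% loss is therefore intended.

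**How much of the H1 data could be missing.** The documents do not say at which assessment the 40% applies. Assume that it applies at Assessment 4 (A4) and that all 750 give a baseline: 750 × 4 = 3,000 values, of which 750 × 3 = 2,250 are post-baseline.

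| When the 450 leave | Missing, A1–A4 | Missing, post-baseline | Missing at A4 |
|---|---|---|---|
| Just after A1 | 1,350/3,000 = 45% | 1,350/2,250 = 60% | 60% |
| Just after A2, or evenly over the three gaps | 900/3,000 = 30% | 900/2,250 = 40% | 60% |
| Just after A3 | 450/3,000 = 15% | 450/2,250 = 20% | 60% |

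If the 40% refers to a later assessment (the schedule runs to Assessment 8), loss at A4 may be below 60%, by an amount the documents do not give.

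**Bias at A4.** Let p be the loss fraction, taken as equal in both arms, and let each arm's departure be the mean difference between its leavers' true scores and the model's prediction for them. Treating time as categorical:

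bias = p × (departure in GSA-ASPIRE-Network − departure in ASPIRE).

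The documents give no value for the gap in brackets. For an assumed gap of 0.5 SD, with SD 0.5:

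| Loss at A4 | Bias (SD) | Bias (points) |
|---|---|---|
| 10% | 0.10 × 0.5 = 0.05 | 0.025 |
| 30% | 0.30 × 0.5 = 0.15 | 0.075 |
| 60% | 0.60 × 0.5 = 0.30 | 0.15 |

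**Against the planned effect.**
- Planned difference: 1.3 − 0.17 = 1.13 points; 1.13/0.5 = 2.26 SD.
- Illustrated bias at 60% loss: 0.15/1.13 = 13% of it.
- Gap needed to cancel it at 60% loss: 1.13/0.60 = 1.88 points; 1.88/0.5 = about 3.8 SD.

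**Against a smaller effect (assumed, not from the documents).** An observed difference of 0.30 points is cancelled at 60% loss by a gap of 0.30/0.60 = 0.50 points, or 1.0 SD. One of 0.15 points is cancelled by a gap of 0.15/0.60 = 0.25 points, or 0.5 SD.

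**The case against.** The strongest reply is that a mixed model already handles dropout. If an adolescent's intention failed to fall and this was recorded at A2 or A3 before leaving, a likelihood fit conditions on it and no bias follows. That stands. A reader might infer that heavier loss of such adolescents from the team arm would by itself create a false effect. It would not: leaving must depend on unobserved intention after that conditioning, and differently by arm.

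A reader might also infer that most of the primary-outcome data will be missing. The documents do not support this. Up to 60% applies to the final assessment; across A1–A4 the share is 15% to 45% under the stated assumptions. The 450 are also described only as participants who may discontinue. The interview target, set as a share of the final 300 and held after time 4, leans towards retention being counted at A4 but does not settle it.

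No document reports differential loss. Participants are not told the basis of the grouping, the assessment payments do not differ by arm through A4, and teams could improve retention, so the direction of any bias is open. Covariate-constrained randomisation lists the proportion of users and intenders among its example club characteristics. That may balance clubs at baseline, but it does not act on loss after randomisation.

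Finally, the 0.5 SD gap is illustrative, and at the planned effect it would not overturn H1. All of this limits the point. None of it supplies a stated assumption or a check.

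**Conclusion.** The point holds in a limited form. The plan expects 450 of 750 adolescents to be lost, uses this only to reach 800, and rests H1 on a missing-at-random assumption that it neither states nor tests.

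The final intention score may be missing for up to 60% of participants. The resulting bias is the loss fraction times an unknown between-arm gap: 0.30 SD (0.15 points) for an assumed gap of 0.5 SD at 60% loss. This rests on the 40% applying at A4, equal loss in both arms, and leaving that depends on unobserved intention.

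A reader might infer that the planned result is unsafe. The figures do not support that, since a difference of 1.13 points would need a gap of about 3.8 SD to cancel. The exposure is a modest observed effect, or the reported size of a larger one.

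**What to change.** In Section 7, Quantitative data analysis for Study 2:

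1. Keep the mixed model as primary, on all adolescents in randomised clubs with any available data. State the missing-at-random assumption and the assessment to which the 40% retention refers.
2. Add time-1 tobacco-use status and its interaction with time. This is already collected.
3. Report retention by arm, club and time-1 at-risk status.
4. Add a delta-adjusted multiple-imputation sensitivity analysis that respects clustering by club (the plan assumes "intra-class correlation (ICC) of 0.3"). Shift unobserved intention in GSA-ASPIRE-Network relative to ASPIRE in both directions, extend the shifts until H1 is lost, and report that tipping point. The range cannot stop at 1 SD: at 60% loss a 1 SD shift moves the A4 difference by 0.60 × 0.5 = 0.30 points, well short of 1.13. Report the tipping point without a fixed pass mark for robustness, since the documents give no basis for one.
5. State that records destroyed under Section 9 cannot enter the analysis, and report their number by arm.

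Recruitment, visits and surveys do not change. The cost is protocol wording and a few extra analysis runs. The downside is that a borderline positive result may have to be reported as sensitive to the missing data.
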